Skin biopsies play an essential role in the verification or confirmation of the diagnosis of patients with dermatologic disorders. The punch biopsy, one of the frequently performed types of skin biopsies, is an incisional method that makes use of a cylindrical blade to obtain a specimen with a fuller thickness of the skin as compared to a shave biopsy. It is a procedure that has a low-risk of developing surgical site infections due to the short operative time and shallow wound depth. The most commonly used skin punch sizes range from 2 mm to 6 mm in diameter. Punch biopsies of less than 4 mm in size do not need to be closed with sutures. Obtaining an adequate tissue sample for histopathologic evaluation while preventing patient disfigurement is important.^[1]

Wound healing is a complex biological process where the main goal of clinical intervention is the promotion of tissue restoration.^[2] Acute wounds are wounds that follow a predictable and timely repair process which results in the restoration of sufficient anatomical and functional integrity if healing proceeds normally.^[3] In the pathophysiology of acute wound healing, there are four overlapping phases of the normal wound healing process namely coagulation, inflammation, granulation tissue formation, and remodeling phase. Neutrophils, macrophages, and platelets provide growth factors and provisional matrices that are required for the recruitment of epidermal and dermal cells into the wound bed during the coagulation and inflammatory phases of healing. The proliferative phase begins 3 days after injury and is characterized by increased keratinocyte and fibroblast proliferation, migration, and extracellular membrane synthesis. During this stage, angiogenesis or neovascularization also occurs. The tissue has a granular appearance due to the presence of blood vessels (granulation tissue). Finally, 1 to 2 weeks after injury,

differentiated fibroblastic cells (myofibroblasts) present in the granulation tissue begin to remodel the extracellular matrix. Acellular scar formation is caused by extracellular matrix remodeling followed by apoptosis of resident cells.^[4]

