A study by Estienne and Di Bella compared Granuflex/Duoderm with traditional dressings which made use of hypochlorite irrigation and packing with paraffin gauze in 40 patients for pilonidal fistula. The hydrocolloid dressing was first applied on the third postoperative day after an iodoform gauze pack was removed which was applied in theater. Dressings were changed on alternate days, but was extended to 3-5 days later on and results showed that wounds with hydrocolloid dressings had complete healing in an average of 6 weeks compared with 10 weeks with the traditional dressings.^[7]

Michie and Hugill compared Granuflex/Duoderm Extra Thin hydrocolloid dressing with an impregnated gauze (Xeroform) in 28 patients with 40 wounds after an elective surgery to assess the effects of the dressings on incisional healing. One-half of every incision was covered with each of the dressings under investigation as each patient served as their own control. Wounds were assessed after a period of 2 to 3 days, 7 to 10 days, 4 weeks, and 7 months postoperatively. No incision showed any evidence of infection and during suture removal, hydrocolloid dressings were assessed to contain exudate, protect the wound, and facilitate mobility and personal hygiene more effectively compared with the impregnated gauze dressing. When assessment was done after 4 weeks, scar segments covered with hydrocolloid dressings showed better appearance in terms of color, evenness, and suppleness compared with the Xeroform gauze, however these differences were no longer observed 7 months after the elective surgery.^[8]

A study by Hulten showed that soiling which commonly occurs with wounds dressed with traditional gauze were not observed in 89% of 340 patients who had undergone colorectal surgery with stoma creation and dressed with hydrocolloid. The study also showed that 92% of the patients studied had no wound infections encountered.^[9]

Burns

A report on the use of hydrocolloid dressing in the treatment of burns by Hermans and Hermans in 1984 showed that the use of Granuflex/Duoderm in 24 patients had favorable healing rates compared with those treated with silver sulfadiazine cream in both superficial and deep partial thickness burns.^[10]

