In a study by Wright *et al*, 67 patients with partial thickness burns managed as outpatients were treated with hydrocolloid dressings (Granuflex/Duoderm) versus conventional dressing (Bactigras) to compare the two products. The healing time (median 12 days) were comparable for both products in this study, however the quality of healing was rated “excellent” in 56% of the participants treated with Granuflex/Duoderm versus 11% in the group treated with Bactigras. The authors in this study suggested to use Granuflex/Duoderm as “first-choice dressing in the management of partial skin thickness burns”.^[11]

Traumatic Wounds

A study done by Heffernan and Martin compared Granuflex/Duoderm Extra Thin with a perforated film absorbent dressing in managing 96 patients with lacerations, abrasions and minor operation incisions. The study showed similar results for healing time for both interventions; however, those patients using hydrocolloid dressings experienced less pain, required less analgesia, and were able to carry out activities of daily living without their wounds getting affected.^[12]

Pediatric Wounds

A study done by Schmitt *et al*. compared hydrocolloid dressing with adhesive skin tapes on post-operative wounds in 170 children. Effective skin closure was comparable in both interventions but hydrocolloids were observed to be more secure, remaining in place in 69 children compared with adhesive skin tapes.^[13]

SIGNIFICANCE OF THE STUDY

This study can provide a potential option to promote faster healing of post-operative wounds particularly for skin punch biopsy used in the field of Dermatology.

It will encourage Filipino dermatologists to reduce the routine use of prophylactic topical antibiotics as post-biopsy care heralding better antibiotic stewardship practices.

MAIN OBJECTIVE

The main objective of this study is to determine the efficacy of using hydrocolloid dressing on wound healing of non-sutured post-punch biopsy sites in comparison to gauze dressing impregnated with topical antibiotics (mupirocin ointment) at the Dermatology outpatient department and the private clinics of dermatology consultants of the University of Santo Tomas Hospital.

SPECIFIC OBJECTIVES

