Specifically, this study aims to compare the efficacy of hydrocolloid dressing after 5 days post-punch biopsy by measuring the following parameters: absence or presence of infection, clinical estimate of reepithelialization, clinical estimate of wound closure, scar formation, pigmentation of scar and cosmetic appearance of wound.

METHODOLOGY

A. Study Design

This is a double blind randomized controlled trial that will be conducted at the outpatient department of the University of Santo Tomas Hospital Department of Dermatology. Permission letters from the Head of Ambulatory Care Services (ACS), the Data Privacy Officer (DPO), and the Medical Director of UST Hospital will be obtained prior to the implementation of this study. Permission letters from the USTH Dermatology consultants for their private patients will be obtained prior to the implementation of this study.

[figure not shown]

Figure 1. Schematic diagram of the study design

B. Patient Selection, Recruitment and Withdrawal

Adult patients 18 to 64 years old with clean cutaneous lesions who will undergo skin punch biopsy using a 3-mm disposable biopsy puncher shall be included in the study.

Patients will be recruited from the UST Hospital outpatient department and from the private clinics of the UST Hospital Dermatology consultants. Patients who have infected wounds, patients who have conditions with poor tendency to heal including diabetes mellitus, peripheral vascular disease, history of keloid formation, patients currently receiving anticoagulation therapy or systemic corticosteroids, and patients known to have hypersensitivity to topical antibiotics shall be excluded from the study.

Participants may request to withdraw from the study at any time. A participant may also be withdrawn from the study if the primary investigator believes that the participant was non-compliant with the treatment guidelines or develops severe and intolerable adverse effects (e.g. hypersensitivity reaction) secondary to the treatment given.

C. Randomization and Blinding

Randomization

Assignment of participants to the experimental (hydrocolloid dressing) or control group (topical antibiotic) will be done using the fishbowl method by a research assistant.

Blinding

Participants and the physician assessors will be blinded with the treatment assigned.

D. Baseline Data Collection

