On the first visit, informed consent will be obtained from the patient. Afterwards, the following data will be recorded by the primary investigator on the baseline general information sheet: study code assigned to each individual patient, age, sex, and anatomic sites involved.

Photographs will be limited to the skin punch biopsy sites and will be taken at baseline using a DSLR camera with uniform distance (3 inches) and lighting.

On the 5th day after the skin punch biopsy procedure, the following data will be recorded by the physician assessors: the presence or absence of infection, the clinical estimate of reepithelialization, the clinical estimate of wound closure, scar formation, pigmentation of scar, and the cosmetic appearance of the wound. The primary investigator will then collect the wound evaluation sheets from the physician assessors. Photographs of the biopsy site will also be taken.

E. Intervention

Before the biopsies will be performed, the sites will be cleansed with 70% isopropyl alcohol and anesthetized intradermally with 1% lidocaine hydrochloride.

No suture, electrocautery, aluminum chloride or other hemostatic agents will be applied to the biopsy sites to avoid inhibition of wound healing inherent with these agents.

Once bleeding will be controlled by pressure, wounds will be dressed with either a 1-inch size Duoderm Control Gel Formula hydrocolloid dressing or gauze dressing impregnated with mupirocin ointment covered by a transparent dressing (Tegaderm). Dressings will be left in place for 5 days, after which the dressings will be removed and will be cleansed with water to remove any exudate.

F. Assessment

For this study, wound assessment will be done after 5 days. Dermoscopy and photographs of the wounds will be taken for every evaluation.

According to a study entitled “Pathophysiology of Acute Wound Healing” by [name] et. al. published in Elsevier Clinics in Dermatology in 2007, there are three phases of wound repair that overlap in time. These are the inflammatory reaction phase, proliferation phase, and remodeling phase. Days after initial injury, the wound would be in the proliferative phase where there would be reepithelialization of the wound, the establishment of appropriate blood supply, and reinforcement of the injured dermal tissue.^[14]

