The possible side effect of hydrocolloid dressing is irritation of the skin. Treatment on patients who will experience any adverse side effects will be immediately stopped.

To minimize the risk of COVID-19 exposure, all safety measures in accordance with the IATF guidelines will be observed.

BENEFITS

The benefit that the patient will acquire from this study is better clinical outcomes of the post-biopsy site. This study can also help reduce medical costs and patients are suggested with alternative options which can be potentially used as one of the treatment modalities for post-biopsy sites.

INCENTIVES AND COMPENSATION

All of the dermatologic consultations and medications of the participants for the duration of the study will be free of charge. Transportation allowance of PHP 100.00 will be provided to the participant on their visit on the 5th day. Management, consultation, and treatment of adverse effects resulting from the participation in this study will be free of charge. No other form of monetary compensation will be provided to the patients for their participation. Patients will be informed of the results of the study once it has been completed.

SCORING CRITERIA FOR EVALUATION OF WOUND

Objective assessment is based on a study by Armstrong et. al. in 1986 entitled "Punch biopsy wounds treated with Monsel's solution or a collagen matrix".^[16] For this study, the assessment will be done as follows:

(1) infection (absent, millimeters of surrounding erythema or equivocal findings; or present, as inferred by indurated erythema or purulent discharge);

- (2) clinical estimate of reepithelialization (rated on a scale of (a) 0% to 25%, (b) 26% to 50%, (c) 51% to 75%, and (d) 76% to 100%);
- (3) clinical estimate of wound closure (rated on a scale of (a) 0% to 25%, (b) 26% to 50%, (c) 51% to 75%, and (d) 76% to 100%)
- (4) scar formation (unhealed; depressed or atrophied; normal fine-line scar; or hypertrophied scar or keloid);
- (5) pigmentation of scar (indeterminate or unhealed; normal; hyperpigmented; or hypopigmented);
- (6) cosmetic appearance of wound (acceptance of patient: indeterminate or unhealed; poor; fair; good; excellent)

DUMMY TABLES

Table 1. Baseline demographic and clinical characteristics

	Total	Hydrocolloid	Topical	P-value
		Dressing	Antibiotic	
Frequency (%); Mean \pm SD				
Age, years				
Sex				
Male				
Female				
Indications for Skin				
Punch Biopsy				
...				

Table 2. Scoring Criteria for Evaluation of Wound

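### Infection is scored only from signs present at the single day-5 examination, so infections that cleared before then, or that occur in participants who leave, are not counted, and nothing after day 5 is observed

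*Combined protocol and SAP*

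**What the plan says.** The Specific Objectives tie every parameter, infection included, to one time point, 5 days after the biopsy. Section D (Baseline Data Collection) gives the recording rule for infection, the first of the six parameters it lists: "On the 5th day after the skin punch biopsy procedure, the following data will be recorded by the physician assessors: the presence or absence of". Section F (Assessment) repeats it: "For this study, wound assessment will be done after 5 days".

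The scoring criteria define the item as "infection (absent, millimeters of surrounding erythema or equivocal findings; or present, as inferred by indurated erythema or purulent discharge". That describes what is seen at the examination. It has no time window and no element of history, and equivocal findings count as absent. Dummy Table 2 has two rows for infection, Absent and Present.

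On dressings, section E (Intervention) states: "Dressings will be left in place for 5 days, after which the dressings will be removed". No inspection during those 5 days is described. Day 5 is the last visit named (Incentives and Compensation), and no later contact is described.

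The Safety Evaluation takes place at the follow-up visit. It asks about itching, burning and stinging, and the primary investigator looks for other signs of adverse effects. Section B allows withdrawal, the Risks section stops treatment for adverse effects, and the statistical section says that missing values will not be imputed. The Significance of the Study says the trial will encourage dermatologists to "reduce the routine use of prophylactic topical antibiotics as post-biopsy care".

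**The concern.** For a question about prophylaxis, the quantity of interest is whether a wound became infected during a stated period. The plan instead records whether signs are visible at one examination. The two differ whenever an infection comes and goes before that examination, occurs in someone who is not examined, or starts later.

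If the share of infections visible on day 5 is the same in both arms, the counts and the difference between arms shrink in the same proportion. If the share differs between arms, for instance because participants leave one arm more often after a reaction, the comparison is also biased, in a direction that cannot be known in advance. In either case a table with few or no infections could be read as reassurance about omitting the antibiotic, which a single look cannot provide.

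**Working it through.** **Step 1. Trace each kind of infection through the plan as written.**

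| Course of infection | How it is recorded |
|---|---|
| Arises before day 5, signs persist on day 5 | Present |
| Arises before day 5, signs cleared by day 5 | Absent |
| Arises before day 5, participant withdrawn or does not attend | Missing, not replaced |
| First appears after day 5 | Absent (not observed) |

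Only the first row is counted. The safety check does not rescue the others: it is held at the follow-up visit, does not list interim infection, early dressing removal or antibiotic use, and is not linked to the infection item in Table 2.

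**Step 2. Reproduce the plan's sample size.** Inputs from the statistical section: means 8.38 and 7.23, SD 1.5, two-sided 5%, 80% power. The difference is 8.38 − 7.23 = 1.15. The noncentral t calculation gives power 0.789 at 27 per arm and 0.804 at 28, so 28 per arm (56 in total) is confirmed. This figure rests on the scar score; infection was not used to size the trial.

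**Step 3. Show what incomplete capture could do.** The documents give no infection rate for punch biopsies, so the true risks and the share *c* of infections visible on day 5 are assumptions. *c* is taken as equal in both arms. Expected cases per arm = 28 × *c* × risk. Power is for the two-sided Fisher test at 0.05, by exact enumeration at 28 per arm.

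| Assumed true risks | *c* = 1 | *c* = 0.75 | *c* = 0.5 | *c* = 0.33 |
|---|---|---|---|---|
| 5% v 30%: expected cases | 1.4 v 8.4 | 1.05 v 6.3 | 0.7 v 4.2 | 0.5 v 2.8 |
| 5% v 30%: power | 58% | 35% | 14% | about 3.5% |
| 5% v 20%: power | 21% | 10% | 2.9% | 0.6% |
| 5% v 15%: power | 8% | 3.4% | 0.8% | 0.1% |

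Example: 28 × 0.5 × 0.30 = 4.2.

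The first column matters as much as the others. Outside the extreme contrast, power is low even with full capture. With no infections in one arm, the other needs 6 of 28 for p < 0.05 (6 v 0 gives p = 0.023; 5 v 0 gives p = 0.0515).

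**Step 4. What a result of no infections would mean.** With 0 of 28 in an arm, the one-sided 95% upper limit solves (1 − p)^28 = 0.05, so p = 1 − 0.05^(1/28) = 10.1%. That limit applies to infection visible on day 5. If only half of all infections are visible then, it corresponds to a cumulative risk of about 10.1% / 0.5 = 20%.

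**The case against.** The strongest reply is that day-5 status is a declared choice. The objective names the time point, infection is one of six parameters, and the Project Summary gives overall healing as the primary outcome. The antibiotic sentence is an aspiration under Significance, not a hypothesis. This stands as a limit on weight: the stated primary outcome is not affected.

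The early-clearing path is also narrow, since signs must appear and settle within 5 days under a dressing meant to stay on. That stands. A reader might infer that every infection arising before day 5 is scored absent. The documents do not support that: persisting signs are scored present, and participants who leave become missing.

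Two passages may tempt a reader to infer that infections after day 5 are likely, and neither shows it. The Background says remodelling begins "Finally, 1 to 2 weeks after injury", but that dates tissue repair, not infection, and the same section calls punch biopsy a low-risk procedure for infection. The literature review says of an earlier hydrocolloid incision study: "Wounds were assessed after a period of 2 to 3 days, 7 to 10 days, 4 weeks, and 7 months postoperatively". It does not say that each visit was meant to look for infection, and it reports none in any incision. The Background does assert high local infection rates, but without a figure.

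Finally, the power table depends on chosen risks and mostly reflects the small sample. That stands as well.

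None of this closes the gap in Step 1. The investigator's check for other signs and the free care for adverse effects are partial safeguards, but neither enters the infection outcome.

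**Conclusion.** The concern holds as a gap in how infection is ascertained. As written, the plan does not count an infection that cleared before day 5, loses one in a participant who leaves, and does not observe any after day 5. The result therefore cannot carry a general statement about prophylaxis after biopsy.

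The size of the loss cannot be estimated from the documents. The fall in power from 58% to 14% rests on assumed risks of 5% and 30%, an assumed 50% visibility on day 5, and equal capture in both arms. A reader might infer that complete capture would let the trial settle the infection question. It would not: at 5% v 15%, power is about 8% with every infection counted. The point bears on the infection parameter and the stewardship statement. It is worth correcting because the remedy is cheap.

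**What to change.** 1. In section D and in the scoring criteria, define the infection outcome as any infection from biopsy through day 5. Ascertain it at the existing day-5 visit by the examination plus a short standard question set and a record check covering infection signs, early dressing removal and any antibiotic started for the site.
2. Count infections known to have occurred in withdrawn participants as events, and report by arm how many participants have unknown status.
3. In Table 2, report the day-5 examined sign as a separate component beside the wider outcome.
4. In the Significance section, limit the infection and prophylaxis statement to infection up to day 5.

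The cost is one question set, a record check at a visit that already takes place, and a few lines of text. The drawback is that the interim component rests partly on patient report and records and is not seen by the assessors, which is why item 3 keeps the examined sign separate. A telephone or chart check at about day 14, reported as its own count, is an optional addition (56 short contacts). It is not needed if the statement is limited as in item 4.

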**A Double-Blind Randomized Controlled Trial on the Efficacy of Hydrocolloid
Dressing vs. Topical Antibiotic on Wound Healing of Post-Punch Biopsy
Wounds Among Patients in a Tertiary Hospital in Manila**

[name] [name]

[name], FPDS

University of Santo Tomas Hospital, [name]

Department of Dermatology

TITLE: A Double-Blind Randomized Controlled Trial on the Efficacy of Hydrocolloid Dressing vs. Topical Antibiotic on Wound Healing of Post-Punch Biopsy Wounds Among Patients in a Tertiary Hospital in Manila

[name], [name]

Resident, Department of Dermatology; Consultant, Department of Dermatology

PROJECT SUMMARY

Rationale:

Objectives: The main objective of this study is to determine the efficacy of using hydrocolloid dressing on wound healing of post-punch biopsy wounds vs topical antibiotic. Specifically, it aims to measure the following parameters: the presence or absence of infection, the clinical estimate of reepithelialization, the clinical estimate of wound closure, scar formation, pigmentation of scar, and the cosmetic appearance of the wound.

Methodology and Population: The study is a double-blind randomized controlled trial which will be conducted at the Dermatology outpatient department and the private clinics of dermatology consultants of the University of Santo Tomas Hospital. Patients who will be included are those who are 18 to 64 years of age with clean cutaneous lesions. Excluded from this study are those who have infected wounds, those who have conditions with poor tendency to heal including diabetes mellitus, peripheral vascular disease, history of keloid formation, those currently receiving anticoagulation therapy or systemic corticosteroids, and those known to have hypersensitivity to topical antibiotics.

Time Frame: 6 months

Expected Outcomes: The primary outcome measure is the proportion of patients who achieved better overall healing when treated with hydrocolloid dressing.

GENERAL INFORMATION**PROTOCOL TITLE:**

**A DOUBLE-BLIND RANDOMIZED CONTROLLED TRIAL ON THE
EFFICACY OF HYDROCOLLOID DRESSING VS. TOPICAL ANTIBIOTIC ON
WOUND HEALING OF POST-PUNCH BIOPSY WOUNDS AMONG
PATIENTS IN A TERTIARY HOSPITAL IN MANILA**

NAME AND ADDRESS OF SPONSOR/FUNDER:

NOT APPLICABLE

NAME AND ADDRESS OF AUTHORS:

[name] [name]

[name], FPDS

University of Santo Tomas Hospital, [name]

BACKGROUND

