Three physician assessors who will be trained in the evaluation of skin punch biopsy wounds and the scoring criteria that will be used in this study will assess the wound and record their evaluations individually.

SAMPLE SIZE AND STATISTICAL ANALYSIS

Using G*Power 3.1.9.7, a minimum of 56 patients or 28 per group are required for this study based on the 8.38 mean Scar appearance score on Hydrocolloid

dressing versus 7.23 mean Scar appearance score on Conventional daily dressing.^[15] This computation also accounts for desired 1.5 common standard deviation, 5% level of significance and 80% power.

Descriptive statistics will be used to summarize the demographic and clinical characteristics of the patients. Frequency and proportion will be used for categorical variables and mean and SD for normally distributed continuous variables. Independent Sample T-test and Fisher's Exact/Chi-square test will be used to determine the difference of mean and frequency, respectively, between patients undergoing Hydrocolloid Dressing versus Topical Antibiotic. All statistical tests will be two tailed tests. Shapiro-Wilk test will be used to test the normality of the continuous variables. Missing values will neither be replaced nor estimated. Null hypotheses will be rejected at 0.05 α -level of significance. STATA 13.1 will be used for data analysis.

Inter-rater and Intra-rater reliability will also be conducted.

SAFETY EVALUATION

Assessment of possible adverse effects due to the hydrocolloid dressing or the topical antibiotics will be done on follow-up visit. Complaints of pruritus, burning, or stinging sensation will be asked from participants, while other physical signs and symptoms of adverse effects to the treatment applied will be checked by the primary investigator.

ETHICAL CONSIDERATIONS

This study will be conducted in accordance with the accepted ethical research practices of the ICH Good Clinical Practice regulations and guidelines. The study will

be explained thoroughly to the eligible patients prior to enrollment. Free and informed written consent will be obtained.

INFORMED CONSENT

All participants involved in the study will not be compromised in terms of treatment. All possible benefits and side effects of the treatment will be fully explained and must be understood by the patients prior to enrollment into the study.

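### The sample size is for a mean scar score the trial does not collect, so its 80% power applies to no planned efficacy test

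*Combined protocol and SAP*

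**What the plan says.** - **Sample Size and Statistical Analysis, sizing:** "a minimum of 56 patients or 28 per group are required for this study based on the 8.38 mean Scar appearance score" with hydrocolloid, against 7.23 with conventional daily dressing in a cited study. The common SD is 1.5, with "5% level of significance and 80% power". All tests are two-sided.
- **Same section, analysis:** a t-test and Fisher's exact or chi-square "test will be used to determine the difference of mean and frequency, respectively". Neither is tied to a named outcome. "Null hypotheses will be rejected at 0.05", with no ordering of outcomes and no adjustment.
- **Project Summary, Expected Outcomes:** "The primary outcome measure is the proportion of patients who achieved better overall healing when treated with hydrocolloid dressing". Specific Objectives lists six parameters side by side and names none as primary.
- **Scoring Criteria for Evaluation of Wound:** all six items are categories. One is "clinical estimate of reepithelialization (rated on a scale of (a) 0% to 25%, (b) 26% to 50%, (c) 51% to 75"%, plus a fourth band up to 100%. The item closest to a scar appearance score is "cosmetic appearance of wound (acceptance of patient: indeterminate or unhealed; poor; fair; good; excellent".
- **Table 2 (dummy):** all six items appear as frequencies with a p-value. There is no mean, total or composite row.
- **Assessment (F):** three trained physicians "will assess the wound and record their evaluations individually". Inter- and intra-rater reliability are planned, but no rule turns three ratings into one value per patient.

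**The concern.** The variable used for sizing, the named primary outcome and the planned tables are three different things. A 1.15-point difference in means needs a numeric score in each patient, and the documents show none. Age is the only continuous variable named in the dummy tables, so the t-test has no efficacy variable to act on. The named primary outcome has no threshold, component item, expected rate or table row.

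Two things are at stake. Readers would take a null result as coming from a trial with 80% power for its main comparison, although that figure was worked out for something else. And because the primary outcome cannot be computed as written, what remains is six p-values of equal standing. Better healing could then be defined after the data are seen, from whichever item looks favourable. The protocol hopes the result will reduce routine prophylactic antibiotic use, so both matter.

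**Working it through.** **1. The plan's own figure.** Inputs from the sample size section: means 8.38 and 7.23, SD 1.5, two-sided 0.05, power 0.80.

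d = (8.38 − 7.23)/1.5 = 1.15/1.5 = 0.767.

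The noncentral t-test needs 27.70 per group, rounded up to 28. Power is 78.9% at 27 and 80.4% at 28. A one-sided test would need only 22. The section does not name the t-test beside the calculation, but the inputs and the match at 28 leave little doubt.

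**2. The same effect on a binary endpoint.** The documents give no rates, so the control rates p_c are assumptions. The effect is carried over as a latent normal shift, p_e = Φ(Φ⁻¹(p_c) + 0.767). Power is by exact binomial enumeration at 28 per group, two-sided 0.05, with uncorrected chi-square.

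| p_c | p_e | Power, Fisher | Power, chi-square | Difference for 80%, Fisher | Difference for 80%, chi-square |
|---|---|---|---|---|---|
| 0.20 | 0.470 | 0.486 | 0.591 | 0.389 | 0.353 |
| 0.30 | 0.596 | 0.495 | 0.601 | 0.404 | 0.371 |
| 0.40 | 0.696 | 0.495 | 0.601 | 0.391 | 0.364 |
| 0.50 | 0.778 | 0.494 | 0.596 | 0.365 | 0.339 |
| 0.60 | 0.846 | 0.439 | 0.554 | 0.334 | 0.310 |
| 0.70 | 0.902 | 0.339 | 0.476 | 0.287 | 0.259 |

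At a 50% control rate, 80% power therefore needs 0.50 + 0.365, about 87% (Fisher), or 0.50 + 0.339, about 84% (chi-square).

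Keeping 80% power for the carried-over effect would take 49-67 per group (Fisher) or 44-58 (chi-square). Exact power does not rise smoothly with n. The chi-square lower end of 44 is where power stays at or above 80%; at control rates of 30% and 40% it first touches 80% at 41.

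**3. Without carrying d over.** Assume control rates of 30-60%, with chi-square power and the sample sizes by normal approximation. A 20-point difference has 22-28% power (Fisher) or 32-37% (chi-square) at 28 per group, and 80% needs 82-97 per group. A 30-point difference has 51-66% or 62-75%, and 80% needs 32-42 per group.

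**4. Four ordered categories.** Latent shift 0.767, 30,000 simulations, six assumed control distributions (%): 25/25/25/25, 40/30/20/10, 10/20/30/40, 50/30/15/5, 5/15/30/50, 5/10/25/60. Power is 35-57% by four-category chi-square and 57-75% by Wilcoxon.

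**5. Six tests at 0.05.** If all six were independent and each attained 5%, the chance of at least one false positive is 1 − 0.95⁶ = 26.5%. Simulation with 20,000 runs, latent correlations 0 to 0.7, Fisher for infection at 3% and chi-square for the rest gave 20.5-22.0% with evenly spread categories. With day-5 clustering (for example 80% in one scar category) it gave 16.4-17.6%.

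**The case against.** The strongest defence is that part of the concern rests on silence. A t-test is planned, the items sit under a heading about scoring, and two are rated on lettered scales. The wound evaluation sheets are not reproduced and the dummy tables are only shells. Numeric coding of cosmetic appearance could have been intended.

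That does not rescue the 80%. Nothing states a coding, Table 2 gives that item frequencies, and its indeterminate or unhealed level has no clear rank. A 1.15-point difference with SD 1.5 comes from another scale and would not transfer to five categories.

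The defence is right on several lesser points:

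- Every power figure for a categorical endpoint depends on assumed rates. The figures illustrate the problem and do not measure this trial. The mismatch itself needs no assumption.
- The 26.5% is an upper illustration. Reepithelialization and closure describe the same wound, and Fisher's test on a rare infection outcome falls well below 5%. Multiplicity is a secondary consequence here.
- The summary speaks of overall healing, so choosing one item narrows the question.
- Keeping N at 56 makes the limits of the trial visible without removing them.
- Withdrawals are allowed and missing values are not replaced, yet no loss allowance is stated. With an assumed 10% loss (25 per group analysed), even the t-test's power falls to 75.7%.

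**Conclusion.** The concern holds and must be fixed before outcome data are seen. The figure of 28 per group is correct for a two-sided t-test on a numeric scar score, but the documents show no such score, so the stated 80% power applies to no specified efficacy test. This conclusion comes from the text alone.

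The size of the shortfall cannot be fixed from the documents. If the planned standardised effect is carried to a binary endpoint with control rates of 20-70%, power is roughly 34-60%, depending on rate and test. Reaching 80% requires a difference of about 26-40 percentage points.

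**What to change.** Amend the protocol and SAP before any outcome data are seen:

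1. **Define one primary outcome from what is collected**, with one value per patient by a stated rule for the three assessors, such as the median category. An example that keeps a proportion is the share of patients with day-5 reepithelialization of 76-100%, compared by Fisher's exact test at two-sided 0.05. An alternative is the four ordered categories compared by a Wilcoxon rank-sum test, which must be added to the plan and had more power than the four-category chi-square under the same assumptions. If overall healing is to stay the question, write an explicit responder rule across named items and size it in the same way.
2. **Make the remaining items secondary**, either Holm-adjusted or descriptive. State who rates cosmetic appearance: the criteria describe it as the patient's acceptance, while Baseline Data Collection has the physicians record it, so the assessor rule may not suit it.
3. **Replace the 80% power sentence** with what the chosen endpoint and single chosen test can detect, labelling assumed rates. For example: assuming 50% in the control arm and 28 analysed per group, the trial has 80% power to detect about 87% by Fisher's exact test. Give the figure for the number expected to be analysed if losses are foreseen.

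The cost is wording only. N can stay at 56, because the documents give no rate from which to re-size. The stated power becomes less favourable, five items lose equal standing with the primary, and a binary cut-point discards information that the ordered categories would keep.
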